6.4.3 Pharmacokinetic Analysis

Each subject will have a single (not serial) plasma PK completed at the end of their week 1 visit. The plasma PK of ISIS 304801 following extensive sampling will be assessed at Week 16 (Week 1 OLE) for all subjects, and Weeks 32 (Month 4 OLE). Additionally, plasma trough levels throughout the 16-week and 12-month OLE treatment period and post-treatment levels during the 12-week follow up period will be measured. Details are given in Appendices A and C.

For all patients who receive ISIS 304801 treatment, non-compartmental PK analysis of ISIS 304801 will be carried out on each individual subject data set. The maximum observed drug concentration (C_{max}) and the time taken to reach C_{max} (T_{max}) will be obtained directly from the concentration-time data. Partial areas under the plasma concentration-time curve from zero time (predose) to selected times (t) after the SC administration (AUC_t) will be calculated using the linear trapezoidal rule. The plasma disposition half-life associated ($t_{1/2\lambda_z}$) with the apparent terminal elimination phase will be calculated using a non-compartment method, if appropriate, using available data (Week 68 and later), from the equation $t_{1/2\lambda_z} = 0.693/\lambda_z$, where λ_z is the rate constant associated with the apparent terminal elimination phase. A minimum of three data points will be used to define λ_z and the correlation of determination values (r^2) had to be at or greater than 0.8 for the estimate to be accepted. The samples at Week 68 (assumed pre-dose value for Week 69), Week 74, and Week 80 will be used to calculate the half-life. Other pharmacokinetic parameters, as appropriate, may be determined or calculated at the discretion of the pharmacokinetic scientist.

Plasma concentrations and PK parameters will be summarized with and without stratification by immunogenicity status using descriptive statistics. Additional details regarding the PK analysis will be described in the Statistical Analysis Plan.

Potential relationships between selected PD and PK measures may also be explored, where deemed appropriate.

6.4. 4 Immunogenicity Analysis

Immunogenicity (IM) results (screen positive/negative, confirmed positive/negative or unevaluable, and when applicable, titer of anti-ISIS 304801 antibodies) before, during, and after treatment with study drug (ISIS 304801) (i.e., sample ADA status) will be listed by treatment and study day. Subject ADA status (positive/negative or unevaluable) for all evaluable patients, along with the study day associated with the first positive IM status emerged (T_{first} , i.e., onset of ADA development), the last positive IM status observed (T_{last}), the duration of ADA response (number of days between T_{first} and T_{last}) if appropriate, the last ADA sample collection day, and subject maximum titer if applicable, will be listed by treatment and study day.

Additionally, the sample and subject IM incidence (number) and incidence rate (percent) will be summarized as the total number and percent of evaluated subjects with antibody negative, positive, and unknown status by treatment. Furthermore, onset, duration, and titer of the ADA response, if applicable, will be summarized as median and range.

Additional details regarding the immunogenicity data analysis will be described in the SAP.

6.4.5 Safety Assessments

1. Liver function, Kidney function, Platelets, LDL, and coagulation tests (detailed in Appendix B): Monitoring of the above (except for platelets) will be performed every 4 weeks for the first 6 months of treatment, and every 8 weeks thereafter, per the Study Schedule (Appendix A). Platelets will be monitored every week for the duration of the study.
2. Self-monitoring of blood glucose: In subjects with diabetes, a home glucometer will be distributed to patients who do not have one already at the first inpatient visit for home-based glucose monitoring (“Self-Monitored Plasma Glucose” or SMPG). Training on the use of the glucometer will be provided as needed. Fasting SMPG will be self-measured in the fasting state: daily if the patient is on insulin therapy, and weekly if on oral antidiabetic therapy.
3. Urinalysis: Urinalysis and urine protein to creatinine ratio will be conducted as per the Study Schedule (Appendix A).
4. Echocardiogram: Echocardiography for assessment of left and right ventricular function and mitral and aortic valve function will be conducted per the Study Schedule (Appendix A). Cardiologists reviewing echocardiograms at NIH will not be aware of treatment assignment during the randomized period. Results will be provided to the DSMB for their review.

5. **EKG:** Standard 12-lead EKGs will be performed after the patient has been resting in a supine position for at least 5 minutes per the Study Schedule (Appendix A).
6. **Troponin T:** Cardiac troponin T will be measured per the Study Schedule (Appendix A).
7. **Pregnancy test:** Pregnancy tests will be performed on female patients with reproductive potential at each inpatient visit.
8. **Pancreatitis:** All patients will be given an instruction card that must be presented to the treating physician if a suspected case of pancreatitis occurs. The card will explain that the patient is in a clinical trial and that serum lipase and/or amylase measures should be done in order to adjudicate the event, based on Atlanta Classification⁵¹. If serum or amylase activity is less than 3 x ULN, imaging, preferably contrast-enhanced computed tomography (CT), should be considered to confirm the diagnosis of acute pancreatitis per the Atlanta Criteria.

7. Human Subject Protection

7.1 Data and Safety Monitoring Plan

Safety data will be monitored on ***an ongoing basis*** by the Principal Investigator and captured by the Sponsor on the CRF. Appropriately trained personnel will be granted access to Express 5.4, the Electronic data capture system for this trial.

At least monthly, the Principal Investigator or designee will review vital signs (including at a minimum heart rate, systolic and diastolic blood pressure), adverse events (including all pre and post dosing adverse events), serum chemistry (including at a minimum alanine aminotransferase, aspartate aminotransferase, alkaline phosphatase, total bilirubin, blood urea nitrogen, and creatinine), coagulation (including at a minimum aPTT, PT, and INR), and urinalysis (including at a minimum urine protein (by dipstick), urine blood, and urine white blood cells). At least weekly, the Principal Investigator or designee will review hematology (at a minimum hemoglobin, absolute lymphocytes, absolute neutrophils, platelet count, WBCs) to advise on possible medication dose changes for safety reasons.

The Ionis Medical Advisor will answer queries and provide safety management recommendations to the Principal Investigator as needed. Anticipated AE's are fully described in the Investigator Brochure. Any safety issues identified in other apoC-III clinical trials will be promptly communicated by the Ionis to the Principal Investigator.

A monthly cumulative summary safety report for all apo-CIII studies, including the current study, will be issued by Ionis Pharmaceuticals, including an assessment of fatal cases, SAEs, treatment discontinuations, treatment-related AEs with severity and relatedness, laboratory analysis, ECG and vital signs. Particular attention will be paid to protocol defined monitoring/stopping rules. This report will be sent monthly to the Principal Investigator and will be used by the Data and Safety Monitoring Board (DSMB) for their ongoing data safety review.

7.1.1 Investigational New Drug application

The investigators will be conducting this study with the oversight of the Food and Drug Administration (FDA) under an Investigational New Drug (IND) application. NIDDK will serve as IND sponsor. Ionis Pharmaceuticals will provide NIDDK with a letter of cross reference authorization to their existing IND for ISIS 304801.

7.1.2 Data and Safety Monitoring Board

A Data and Safety Monitoring Board (DSMB) will be assembled by Ionis Pharmaceuticals and include an NIDDK statistician to review safety, tolerability and efficacy (as needed) data collected on ISIS 304801 during this study. The membership of the DSMB will be determined by the PI in collaboration with the Company. Based on its ongoing assessment of the safety and tolerability of ISIS 304801, the DSMB will provide recommendations to the Principle Investigator for modifying, stopping or continuing the study as planned. The DSMB will meet approximately 3 times per year (exact schedule to be determined by DSMB Chair), and additional ad hoc meetings may be called by the Chair if an imminent significant safety concern arises (e.g. unexpected death of study participant, new serious safety issue identified in the drug development program). Study data (blinded during the initial 4 month placebo controlled period) will be provided to the DSMB via from the study database maintained by Ionis Pharmaceuticals. The NIDDK statistician will have access to the unblinding scheme, and can provide this to the DSMB on request. The Investigator will review and respond to the DSMB recommendations in writing. Any recommendations of the DSMB will not be binding but require due consideration by the Investigator in consultation with the NIDDK/NIAMS IRB. If the DSMB recommends continuation of the study without modification, no formal response will be required. However, if the recommendations request action, such as a recommendation for termination of the study or modification of the protocol, the Investigator will provide a formal written response to the DSMB stating whether the recommendations will be followed and the plan for addressing the issues.

7.1.3 Study monitoring

Study procedures will be subject to audits and/or monitoring visits to ensure compliance with the protocol and applicable regulatory requirements consistent with the NIDDK quality assurance program plan. Audit and/or monitoring visit results will be reported to the Principal Investigator for further reporting as appropriate. Study documents and pertinent hospital or clinical records will be reviewed to verify that the conduct of the study is consistent with the protocol plan.

As required by FDA 21 CFR 312.50 (and NIH OHSRP's SOP 23), trial procedures will be subject to review and/or monitoring visits to ensure compliance with the protocol and applicable regulatory requirements with the NIDDK quality assurance program plan. Audit and/or monitoring visits results will be reported to the Principal Investigator/Sponsor for further reporting to the FDA consistent with applicable regulations. The specific monitoring plan will be developed with the Principal Investigator and frequency of monitoring visits determined by such factors as study enrollment, data collection status and regulatory obligations. Study documents and pertinent hospital or clinical records will be reviewed to verify that the conduct of the study is consistent with the protocol plan.

7.1.4 Adjudication Committees

All SAEs that occur during the study that are consistent with a major acute cardiovascular event (MACE) will be adjudicated by a blinded, independent committee as outlined in the MACE Adjudication Charter.

All AEs and SAEs that occur during the study that are consistent with an event of acute pancreatitis will be adjudicated by a blinded, independent committee according to the Atlanta classification of acute pancreatitis⁵¹ and as outlined in the Pancreatitis Adjudication Charter. In addition, data for prior episodes of acute pancreatitis or suspected pancreatitis will be collected by review of each patient’s medical chart and these events will also be adjudicated.

7.2 Adverse Events, Protocol Deviations, and Unanticipated Problems

The collection, monitoring and analysis of adverse events will be the responsibility of the Principal Investigator and the investigative team.

7.2.1 Definitions

Adverse events, protocol deviations, unanticipated problems (UP), serious adverse events, sponsor and serious, are defined as described in NIH HRPP SOP 16 (“Reporting Requirements for Unanticipated Problems, Adverse Events and Protocol Deviations.”) with further details and modifications given below. All adverse events occurring during the study, including those observed by or reported to the research team, will be recorded, and will be summarized for the NIDDK/NIAMS IRB by the investigative team and to the FDA by NIDDK at the time of annual review.

Adverse Event (AE)

An adverse event is any unfavorable and unintended sign (including a clinically significant abnormal laboratory finding, for example), symptom, or disease temporally associated with the Study or use of investigational drug product, whether or not the AE is considered related to the investigational drug product.

Adverse Reaction and Suspected Adverse Reaction

An adverse reaction is any AE caused by the Study Drug. A suspected adverse reaction is any AE for which there is a reasonable possibility that the drug caused the AE. A suspected adverse reaction implies a lesser degree of certainty about causality than an adverse reaction.

Serious Adverse Event (SAE)

A SAE is any AE that in the view of either the Investigator or Sponsor, meets any of the following criteria:

- Results in death
- Is life threatening: that is, poses an immediate risk of death at the time of the event
An AE or suspected adverse reaction is considered “life-threatening” if, in the view of either the Investigator or Sponsor, its occurrence places the patient at immediate risk of death. It does not include an AE or suspected adverse reaction that, had it occurred in a more severe form, might have caused death.
- Requires inpatient hospitalization or prolongation of existing hospitalization
Hospitalization is defined as an admission of greater than 24 hours to a medical facility and does not always qualify as an AE.
- Results in a persistent or significant incapacity or substantial disruption of the ability to conduct normal life functions

- Results in a congenital anomaly or birth defect in the offspring of the patient (whether the patient is male or female)
- Important medical events that may not result in death, are not life-threatening, or do not require hospitalization may also be considered serious when, based upon appropriate medical judgment, they may jeopardize the patient and may require medical or surgical intervention to prevent one of the outcomes listed in this definition. Examples of such medical events include allergic bronchospasm requiring intensive treatment in an emergency room or at home, blood dyscrasias or convulsions that do not result in inpatient hospitalization, or the development of drug dependency or drug abuse

Protocol Deviation:

Any change, divergence, or departure from the NIDDK/NIAMS IRB-approved research protocol. The impact of a PD is characterized by designation as serious or not serious. A protocol deviation is serious if it meets the definition of a Serious Adverse Event (see above) or if it compromises the safety, welfare or rights of subjects or others.

7.2.2 Monitoring and Recording Adverse Events

Any pre-existing conditions or signs and/or symptoms present in a patient prior to the start of the Study (i.e., before informed consent) should be recorded as Medical History and not recorded as AEs unless the pre-existing condition worsened. The Investigator should always group signs and symptoms into a single term that constitutes a single unifying diagnosis if possible.

Serious Adverse Events

The collection of SAEs will begin after the patient signs the informed consent form and stop at the end of the patient’s follow-up period. When the Investigator is reporting by telephone, it is important to speak to someone in person versus leaving a message. An Initial Serious Adverse Event Form should be completed and a copy should be faxed to the Sponsor and to Ionis or designee.

Detailed information should be actively sought and included on Follow-Up Serious Adverse Event Forms as soon as additional information becomes available. All SAEs will be followed until resolution. SAEs that remain ongoing past the patient’s last protocol-specified follow-up visit will be evaluated by the Investigator and Ionis. If the Investigator and Ionis agree the patient’s condition is unlikely to resolve, the Investigator will determine the follow-up requirement.

Non-Serious Adverse Events

The recording of non-serious AEs will begin after the patient signs the informed consent form and will stop at the end of the patient’s follow-up period. The Investigator will monitor each patient closely and record all observed or volunteered AEs on the Adverse Event Case Report Form.

7.2.3 Evaluation of Adverse Events (Serious and Non-Serious)

The Investigator’s opinion of the following should be documented on the Adverse Event Case Report Form:

Relatedness

The event's relationship to the Study Drug (ISIS 304801 or placebo) is characterized by one (1) of the following:

- Related: There is clear evidence that the event is related to the use of Study Drug, e.g., confirmation by positive re-challenge test
- Possible: The event cannot be explained by the patient's medical condition, concomitant therapy, or other causes, and there is a plausible temporal relationship between the event and Study Drug (ISIS 304801 or placebo) administration
- Unlikely/Remote: An event for which an alternative explanation is more likely (e.g., concomitant medications or ongoing medical conditions) or the temporal relationship to Study Drug (ISIS 304801 or placebo) administration and/or exposure suggests that a causal relationship is unlikely (For reporting purposes, Unlikely/Remote will be grouped together with Not Related)
- Not Related: The event can be readily explained by the patient's underlying medical condition, concomitant therapy, or other causes, and therefore, the Investigator believes no relationship exists between the event and Study Drug

Severity

The event's severity is characterized by one of the following:

- Mild: The event is easily tolerated by the patient and does not affect the patient's usual daily activities
- Moderate: The event causes the patient more discomfort and interrupts the patient's usual daily activities
- Severe: The event is incapacitating and causes considerable interference with the patient's usual daily activities

If the event is an SAE, then all applicable seriousness criteria must be indicated.

Action Taken with Study Drug

Action taken with Study Drug (ISIS 304801 or placebo) due to the event is characterized by one of the following.

- None: No changes were made to Study Drug (ISIS 304801 or placebo) administration and dose
- Permanently Discontinued: Study drug was discontinued and not restarted
- Temporarily Interrupted, Restarted – Same Dose: Dosing was temporarily interrupted or delayed due to the AE and restarted at the same dose
- Reduced Dose: Dosing frequency was reduced

Treatment Given for Adverse Event

Any treatment (e.g., medications or procedures) given for the AE should be recorded on the Adverse Event Case Report Form. Treatment should also be recorded on the concomitant treatment or ancillary procedures CRF, as appropriate.

Outcome of the Adverse Event

If the event is a non-serious AE, then the event's outcome is characterized by one of the following:

- AE Persists: Patient terminates from the trial and the AE continues
- Recovered: Patient recovered completely from the AE

- Became Serious: The event became serious (the date that the event became serious should be recorded as the Resolution Date of that AE and the Onset Date of the corresponding SAE)
- Change in Severity (if applicable): AE severity changed

If the event is an SAE, then the event's outcome is characterized by one of the following:

- Ongoing: SAE continuing
- Persists (as non-serious AE): Patient has not fully recovered but the event no longer meets serious criteria and should be captured as an AE on the non-serious AE eCRF (the SAE resolution date should be entered as the date of onset of that AE)
- Recovered: Patient recovered completely from the SAE (the date of recovery should be entered as the SAE resolution date)
- Fatal: Patient died (the date of death should be entered as the SAE resolution date)

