Careful clinical assessment of fat distribution through visual and physical examination can confirm the diagnosis. Patients with FPL have reduced subcutaneous fat in the limbs and truncal regions and may have excess subcutaneous fat deposition in neck, face and intra-abdominal regions. Patients with the Dunnigan variety have normal body fat distribution in childhood and gradually lose subcutaneous fat from the extremities and trunk around the time of puberty. In women, the loss of fat may be most striking in the buttocks and hips. At the same time these patients accumulate fat on the face (“double chin”), neck and upper back (“Cushingoid appearance with buffalo hump”). The extent of adipose tissue loss usually determines the severity of the metabolic abnormalities. Patients display prominent muscularity and phlebomegaly (enlarged veins) in the extremities and complain of disproportionate hyperphagia. The condition in females is more easily recognized than in men, and so is reported more often. Patients may also have a family history of similar physical appearance and/or fat loss. Genetic testing, when available, is confirmatory.^{2,16,18}

Current treatment includes lifestyle modification such as reducing caloric intake and increasing energy expenditure via exercise. Conventional therapies used to treat severe insulin resistance (metformin, thiazolidinediones, GLP-1s, insulin), and/or high TGs (dietary fat restriction, fibrates, fish oils) are not very efficacious in these patients ³.

[figure not shown]
Partial Lipodystrophy is an orphan indication for which there is a significant unmet medical need. Diabetes and/or hypertriglyceridemia associated with this condition can lead to serious complications ¹⁷ such as:

- Acute pancreatitis, especially when triglyceride levels are >1,000 mg/dL
- Accelerated microvascular complications from uncontrolled diabetes
- Accelerated cardiovascular disease from lipid abnormalities and insulin resistance
- Steatohepatitis that can progress to cirrhosis
- Proteinuric nephropathies which can progress to end stage renal disease

In patients with generalized lipodystrophy the metabolic complications are partially related to leptin deficiency, and can be ameliorated in part by leptin replacement. However, leptin deficiency alone cannot explain the severity of metabolic disease in patients with PL who have variable leptin levels. Unpublished

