7.3 Reporting

Serious unanticipated problems and serious protocol deviations will be reported to the NIDDK/NIAMS IRB and Clinical Director as soon as possible but not more than 7 days after the PI first learns of the event. Not serious unanticipated problems will be reported to the NIDDK/NIAMS IRB and Clinical Director as soon as possible but not more than 14 days after the PI first learns of the event. Non-serious protocol deviations will be reported to the NIDDK/NIAMS IRB (as soon as possible but not more than 14 days after the PI first learns of the event) only if they represent a departure from NIH policies for the conduct of human subjects research, adversely affect the health care of the subject(s) or compromise the interpretation or integrity of the research. Non-serious protocol deviations that result from normal subject scheduling variations or technical issues associated with sampling that does not impact the health of the subject or the interpretation of the study data will not be reported.

For studies conducted under an IND, any event that is a serious, unexpected, and suspected adverse reaction (SUSAR) (related to study drug) will be reported by the Investigator to the NIDDK Clinical Director, NIDDK/NIAMS IRB, Food and Drug Administration (FDA), and Ionis Pharmaceuticals as soon as possible **and no later than 7 days** (for a death or life-threatening event) **or 15 days** (for all other SAEs) **after the investigator's or institution's initial receipt of the information.** All serious, unexpected, and suspected adverse reactions (SUSARS) will be reported in aggregate at the time of continuing review.

IND Safety Reports will be submitted to the FDA by NIDDK.

If only limited information is initially available, follow-up reports are required. If an ongoing SAE changes in its intensity or relationship to study drug or if new information becomes available, a follow-up SAE report should be sent to the FDA. All SAEs should be followed to resolution or stabilization.

Deaths will be reported by the investigative team to the NIDDK Clinical Director and NIDDK/NIAMS IRB within 7 days after the PI first learns of the event. All deaths that have occurred among study participants since the previous review will be summarized at the time of continuing review.

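### The 7.2.3 category *Possible* is stricter than the 7.2.1 definition of a suspected adverse reaction, and the four relatedness categories leave a gap that permits under-attribution to the drug.

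*Combined protocol and SAP*

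**What the plan says.** **Definition (7.2.1).** "A suspected adverse reaction is any AE for which there is a reasonable possibility that the drug caused the AE". The section adds: "A suspected adverse reaction implies a lesser degree of certainty about causality than an adverse reaction". Nothing there requires other causes to be ruled out.

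**Categories on the adverse event CRF (7.2.3).** The investigator picks one of four:
- *Related*: "There is clear evidence that the event is related to the use of Study Drug", with a positive re-challenge as the example.
- *Possible*: "Possible: The event cannot be explained by the patient's medical condition, concomitant therapy, or other causes". Plausible timing relative to dosing is a second condition, and both must hold.
- *Unlikely/Remote*: "An event for which an alternative explanation is more likely", or the timing makes a causal link unlikely. This category is merged with *Not Related* for reporting.
- *Not Related*: disease, other therapy or another cause readily explains the event, and the investigator therefore believes there is no relationship.

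**Reporting (7.3).** "any event that is a serious, unexpected, and suspected adverse reaction (SUSAR) (related to study drug) will be reported by the Investigator", within 7 days for a death or life-threatening event and within 15 days otherwise. No section says which of the four categories make an event a suspected adverse reaction.

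**Use of the coding.** The monthly safety report described in 7.1, which the DSMB uses, includes treatment-related AEs with their relatedness. Safety and tolerability is a secondary outcome (4.2.2).

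**The concern.** The CRF scale should put the 7.2.1 definition into practice. Instead, its lowest drug-attributing category asks for something 7.2.1 does not: that no other cause can explain the event. That standard is hard to meet in a disease with many complications of its own. Section 2.1 lists acute pancreatitis, microvascular complications of uncontrolled diabetes, accelerated cardiovascular disease, steatohepatitis and "Proteinuric nephropathies which can progress to end stage renal disease". The protocol monitors or adjudicates liver (7.5.1), renal (7.5.2) and pancreatic (7.5.9, 7.1.4) events and MACE (7.1.4), so the overlap is substantial.

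At stake is whether a drug reaction that resembles the disease is coded as possibly drug-related, is counted as such in the report to the DSMB and, if serious and unexpected, is sent for expedited reporting.

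**Working it through.** The plan states no figure on this point, so the check sets the definitions side by side and sorts cases through them. All cases have plausible timing.

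| Case | 7.2.1: suspected adverse reaction? | 7.2.3 category |
|---|---|---|
| (a) Drug and disease equally credible | Yes, a reasonable possibility exists | None fits |
| (b) Disease somewhat more likely, drug still a reasonable possibility | Yes | *Unlikely/Remote*, reported with *Not Related* |
| (c) Only the drug explains the event | Yes | *Possible* (or *Related* with clear evidence) |

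Case (a), category by category:
1. *Related* fails without clear evidence.
2. *Possible* fails because the disease can explain the event.
3. *Unlikely/Remote* fails because the alternative is not more likely and the timing fits.
4. *Not Related* fails because the investigator does not believe that no relationship exists.

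The investigator must nevertheless tick one box. The two sections agree in case (c) and disagree in (a) and (b).

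**Link to reporting.** The 7.3 trigger uses the 7.2.1 term but adds a parenthesis equating it with being related to study drug. The 7.2.3 pooling rule does not say which reporting it governs. A reader who takes the CRF category as the trigger would not expedite a serious, unexpected event in case (b), or one in case (a) that had been coded downward. A reader who applies 7.2.1 directly would report both.

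**Can the arm comparison make up for this?** Assume the 10 planned completers split 5 and 5, as in 5.1. For an event type seen in one arm only, two-sided Fisher exact p values are:
- 3/5 against 0/5: 2 × C(5,3)/C(10,3) = 2 × 10/120 = 0.17
- 4/5 against 0/5: 2 × C(5,4)/C(10,4) = 2 × 5/210 = 0.048

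Four of five treated patients would need the event, with none on placebo, before the comparison reached 0.05. In the 12-month extension all patients receive active drug (4.1), so there is no concurrent control. Attribution of individual cases therefore carries much of the weight.

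**The case against.** The strongest reply is that missed SUSARs are an inference. Section 7.3 triggers on a term defined in 7.2.1, at a low threshold, and never cites 7.2.3. Non-exhaustive categories leave case (a) to the investigator's opinion; they do not prove a systematic push away from the drug. Much oversight also does not depend on the relatedness code:
- AEs are recorded whether or not considered related (7.2.1).
- SAE forms go to the sponsor and the company with no relatedness condition (7.2.2).
- Deaths and serious unanticipated problems are reported within 7 days (7.3).
- The monthly report also covers fatal cases, SAEs, discontinuations and laboratory results (7.1).
- Pancreatitis and MACE are adjudicated by blinded independent committees (7.1.4).

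All of this stands and limits the harm. None of these steps is stated to reassess causality, however, and the adjudication does not cover liver, renal or glycemic events.

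A reader might infer more: that drug reactions resembling the disease will escape expedited reporting, or that *Possible* is almost unusable for the monitored events. The documents support neither. The 7.2.1 definition remains available to the investigator, and clear evidence can still make an event *Related*. No figure shows how often disease could explain a monitored event. The overlap is also partial. Section 2.1 names complications of uncontrolled diabetes rather than hyperglycemia itself, and its list of complications contains neither low platelets, which have the most detailed rules (7.6.3), nor injection-site reactions, the most frequent AE (2.3.4). How many disease-like events would count as unexpected depends on the Investigator's Brochure, which is not part of these documents.

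**Conclusion.** The point holds as a conflict between two definitions and a gap in the scale. *Possible* is stricter than 7.2.1, case (a) has no category, and case (b) is reported as not related although 7.2.1 makes it a suspected adverse reaction. The wording permits under-attribution in three places: relatedness coding of any AE, the treatment-related counts sent to the DSMB, and expedited reporting. Only serious and unexpected events are exposed to the third.

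The number of events affected cannot be estimated from the documents. The conclusion assumes that an investigator applies the category wording literally; one who works from 7.2.1 would not go wrong on reporting but would still find no correct box for case (a). No estimand, sample size, power or efficacy analysis is affected. The change should be made because the wording governs safety attribution in a small trial and is cheap to correct.

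**What to change.** 1. In 7.2.3, reword *Possible* along these lines: the timing is plausible and there is a reasonable possibility that Study Drug caused the event, even if the patient's condition, another therapy or another cause could also explain it.
2. Restrict *Unlikely/Remote* to events with no reasonable possibility of drug causation. Without this step, case (b) would meet both *Possible* and *Unlikely/Remote* and could still be pooled with *Not Related*.
3. In 7.3, state that *Related* and *Possible* both count as suspected adverse reactions, so that the parenthesis there has a defined meaning.

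With these changes cases (a) and (b) become *Possible*, case (c) is unchanged, and events with no reasonable possibility of drug causation stay in the two lower categories.

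The cost is an edit to the protocol and the CRF guidance, somewhat more events coded as possible, and a few more expedited reports. No analysis changes.
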